8 HEMACHIP

Operational requirements are divided to two periods:

Year 1: During the discovery phase, all tests will be conducted by JaxBio and TAU, which developed and optimized and routinely perform the procedure. At this stage, microarray measurements will be performed on a commercial platform that will be purchased from suppliers such as Agilent / Illumina. All reagents needed for the test will be either purchased or produced in-house.

Blood will be collected by all medical centers in cell-free DNA preservative tubes (STRECK) which stabilizes cell-free DNA for up to 14 days at room temperature. If needed, one ml of the blood will be immediately frozen for genomic DNA extraction. The required blood samples for the discovery phase will be shipped to JaxBio via FedEx. Cell-free tubes will be shipped at room temperature, while frozen blood will be shipped with ice packs to avoid thawing of the sample which may lead to DNA degradation. Import/export issues will be handled by JaxBio or TAU which holds a dedicated import department and has extensive expertise in all importing aspects. At JaxBio/TAU, plasma, serum and buffy coat will be separated, and cell-free DNA and genomic DNA will be extracted. Subsequently, methylation / hydroxymethylation labeling, microarray hybridization, detection and analysis will be performed.

Years 2-3: Throughout the second phase of the project, a custom targeted microarray, HemaChip will be developed and used for all tests. The HemaChip will be developed by Forschungszentrum für Medizintechnik und biotechnologie (FZMB) who specializes in microarray development, manufacturing and distribution. (FZMB) will be responsible for all aspects of distributing the

HemaChip to partners' labs including manufacturing, labeling, shipping etc. At this stage, all partners will purchase the reagents needed for performing the methylation labeling and HemaChip assays. Reagents that are produced at JaxBio/TAU will be validated in-house and shipped to partners' labs along with a validation kit to ensure performance. Quality control measures will be set up to ensure the same analytic condition for all laboratory partners. All tests will be conducted at the clinical sites. Additional validation tests will be conducted by JaxBio and TAU, as needed.

9 REGULATORY AND REPORTING REQUIREMENTS

9.1 Adverse event definition

An AE is any change in physical signs, symptoms, and/or clinically significant laboratory change occurring in any phase of a clinical trial. An AE can therefore be any unfavorable and unintended sign (including abnormal laboratory findings), symptom, or disease related to study procedure.

Disease progression will not be recorded as an AE. Progressive disease (PD) will be captured in a disease evaluation form in the CRF and not in the AE form.

9.2 Adverse events of special interest

Any new malignancy (excluding: FL and MZL transformed to lymphoma, MDS transformed to AML and MGUS or SMM transformed to MM) or active inflammatory disease that requires intervention will require data collection in the eCRF and be recorded in a timely manner, irrespective of seriousness (ie, serious and non-serious AEs) or the time of occurrence during the clinical trial.

9.3 Serious adverse event definition

A serious adverse event (SAE) is any AE occurring that:

- Results in death.
- Is life-threatening. Life-threatening means that the subject was at immediate risk of death from the reaction as it occurred, i.e., it does not include a reaction which hypothetically might have caused death had it occurred in a more severe form.
- Requires in subject hospitalization or prolongation of existing hospitalization. Hospitalization admissions and/or surgical operations scheduled to occur during the study period, but planned prior to study entry are not considered SAEs if the illness or disease

existed before the subject was enrolled in the study, provided that it did not deteriorate in an unexpected manner during the study (e.g., surgery performed earlier than planned). Planned hospitalizations for treatments or evaluations or that are related and expected as the natural course of the underlying hematological condition are also not considered SAEs.

- Results in persistent or significant disability/incapacity. Disability is defined as a substantial disruption of a subject's ability to conduct normal life functions.
- Is a congenital anomaly/birth defect.
- Is an important medical event.
- An important medical event is an event that may not result in death, be life-threatening, or require hospitalization but may be considered an SAE when, based upon appropriate medical judgment, it may jeopardize the subject and may require medical or surgical intervention to prevent 1 of the outcomes listed in the definitions for SAE.

9.4 Adverse events reporting

All (serious) AEs occurred within 24 hours after study procedure and deemed to be related to study procedure(s) and AEs of special interest (see section 9.2) will be recorded in the e-CRF.

Study Medical Monitor must be notified of the occurrence of any SAE within 24 hours of the investigator, designee, or site personnel's knowledge of the event. SAEs will be reported by completing a Serious Adverse Event Form and e-mailing it to the assigned e-mail distribution list within 24 hours of their knowledge of the event, with any supporting documentation (results of relevant investigations, list of concomitant medications etc.). Follow-up must be submitted in a timely fashion as additional information becomes available.

SAE Reporting Contact Information

Email: [contact] AND [contact]

The Investigator, designee or site's personnel will also update the SAE information within the eCRF as part of eCRF data entry requirements.

The study investigator of each study site is responsible for notifying the Institutional Review Board (IRB) or Local Ethics Committee (LEC) in accordance with local regulations, of all SAEs.

9.5 Medical monitoring and safety management

A Medical Monitor will be assigned to oversee the safety of the trial and will be responsible for review of AEs and SAEs and for causality assessment. The Medical Monitor will be a hematology specialist with expertise in clinical trials. The Medical Monitor will not serve as a principal investigator in any of the participating clinical sites.

10 STATISTICAL CONSIDERATIONS

10.1 Study design

Controlled study - This study aims to identify methylation patterns indicating the presence of cancer. Comparison to control participants with no malignant diseases is essential for identifying tumor-specific methylation patterns.

Open study - The current study is an open study where all participants are divided into known groups. For the first stage of the study, the group identification is essential for discovery of biomarkers for each disease type. Discovery stage will be based on empirical comparison between controls and patients diagnosed with various hematological cancers. Therefore, group identification is required for validation, comparison with state-of-the-art diagnosis and disease status.

The current study contains only one type of intervention and therefore randomized/crossover or parallel groups are inapplicable.

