
DURATION OF SUBJECT PARTICIPATION
	
Subjects that serve as controls, subjects at risk (from the Third stage) and a subset of patients from the First and Second stage are expected to donate blood a single time. Following this donation, their participation will end.
 
For a subset of patients, it is expected, after signing the informed consents, that the serial samplings will be performed during the disease follow-up according to the standard clinical practice and/or recommended schedule and disease assessment plan (see Table 3).
 
For enrolled subjects, all have the right to withdraw at any time.
 
All follow-up patients will be followed for a period of up to 36 months.
 
Subjects who complete the main study, may be followed up for their disease status, anti-cancer treatments, concomitant medications, new primary malignancy and survival, following a statistical review of the study results. Serial blood samplings will be performed during the long-term follow-up according to the standard clinical practice and/or recommended schedule and disease assessment plan (see Table 3).

	
A detailed plan for long-term follow-up beyond the main study will be provided as an amendment to this protocol.

EVALUATIONS
	
Classification of a broad spectrum of haematological malignancies based on the detection of epigenetic biomarkers from genomic DNA, cell-free (cf) DNA, exosomal DNA, RNA and non-coding RNA. The identified biomarkers will include proteins, metabolites, and other characteristic biomolecules.
 
Year 1: During the discovery phase, all tests will be conducted by JaxBio and TAU with the aid of technical service providers. At this stage, microarray measurements will be performed on a commercial platform that will be purchased from suppliers such as Agilent / Illumina. All reagents needed for the test will be either purchased or produced in-house.
 
Years 2-3: Throughout the second phase of the project, a custom-targeted microarray, HemaChip will be developed and used for all tests. The HemaChip and custom reagents will be distributed to partners’ labs and all tests will be conducted at the clinical sites and partners labs. Additional validation tests will be conducted by JaxBio and TAU, as needed.

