6.2 Schedule of events

The detailed summary of the evaluations and procedures planned in this study is presented in Tables 2 and 3.

Table 2. Schedule of events

Evaluation	Screening visit¹ (Day -28 to -1)	Baseline sample (Day 1 ± 28 days)	Follow-up visit² (sub-set of patients in Stage 2)
Signed consent form	X		
Assessment of eligibility criteria	X		
Assigning patient ID	X		
Assigning patient barcode	X		
Record medical history ³	X	X	
Record concomitant medications	X	X	X
Record demographics ⁴	X		
Record smoking history / status	X	X	X
Record prior anti-cancer treatments ⁵	X	X	
Record weight	X	X	X
Record heights	X		
Record baseline disease characteristics including prognostic profile ²	X		
MM lab profile for subjects at risk to develop the investigated hematological malignancies ⁶	X		
Blood sampling for central lab (JaxBio) ⁷		X ²	X ²
Disease response evaluation			X ²
Survival status			X
Record adverse events		X	X

¹ Screening visit can be performed at the same day as baseline sample.

² Refer to Table 3 for recommended schedule and disease assessment plan for follow-up patients in Stage 2.

³ Medical history will include details of initial diagnosis.

⁴ Demographics include sex, age and race.

⁵ Only for Secondary-AML, transformed FL and MZL conditions.

⁶ **In Stage 3.** MM lab profile will include SPEP and FLC, full chemistry and CBC.

⁷ Two (2) blood tubes for each sample will be collected and shipped. Refer to Study Manual.

HemaChip tests at the clinical sites ⁸		X ⁹	X ⁹
---	--	----------------	----------------

⁸ **In stages 2 and 3 of the clinical trial only.** The HemaChip and custom reagents will be distributed to partners' labs and all tests will be conducted at the clinical sites.

⁹ Two (2) blood tubes for each sample will be collected. One (1) for test at the clinical sites and the second as a backup for additional validation tests at JaxBio and TAU, as needed. Refer to Study Manual.

Table 3. Recommended schedule and disease assessment plan – Only for follow-up patients

Condition Visit	Baseline Characteristics and Assessments ¹	Follow-up for Disease Evaluation		Blood Sample for Central Lab/HemaChip at site ^{2,3}
		Disease Evaluation ¹	Recommended Schedule	

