7.2 Baseline sample

- Review medical history
- Review concomitant medications
- Review prior anti-cancer treatments
- Record weight
- Record smoking status
- Blood sampling for central lab (JaxBio). Two (2) blood tubes for each sample will be collected and shipped. Refer to study manual.
- Record AEs
- Hemachip tests at the clinical sites - **in stages 2 and 3 of the clinical trial only**. Two (2) blood samples will be collected. One (1) for testing at the clinical sites and the second as a backup for additional validation tests at JaxBio and TAU, as needed. Refer to Study Manual.

7.3 Clinical follow-up – sub-set of patients in Stage 2

- Review concomitant medications
- Record weight
- Record smoking status
- Blood sampling for central lab (JaxBio) - refer to Table 3 for recommended schedule and disease assessment plan. Refer to study manual.

- Record AEs
- Disease response evaluation (for follow-up patients in Stage 2) - refer to Table 3 for recommended schedule and disease assessment plan
- Survival status
- Hemachip tests at the clinical sites - **in stages 2 and 3 of the clinical trial only**. Two (2) blood samples will be collected. One (1) for testing at the clinical sites and the second as a backup for additional validation tests at JaxBio and TAU, as needed. Refer to Study Manual.

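### Section 10.1 keeps validation open without need: Stage 2–3 HemaChip readers are not masked and no rule says which result counts after a backup-tube test, so accuracy can be biased upward

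*Protocol*

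**What the plan says.** **Openness.** Protocol section 10.1 states: "The current study is an open study where all participants are divided into known groups". It explains that Stage 1 needs group labels to find markers, and then concludes: "Therefore, group identification is required for validation, comparison with state-of-the-art diagnosis and disease status".

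**Where the chip is run.** For years 2–3, section 8 says: "All tests will be conducted at the clinical sites. Additional validation tests will be conducted by JaxBio and TAU, as needed". The synopsis (Evaluations) is slightly wider: "all tests will be conducted at the clinical sites and partners labs".

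**Second tube.** Table 2, footnote 9, describes the two tubes: "One (1) for test at the clinical sites and the second as a backup for additional validation tests at JaxBio and TAU, as needed". Sections 7.2 and 7.3 and Table 3, footnote 2, say the same. None of them gives a trigger for using the second tube, or a rule for the case where the two results differ.

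**Follow-up samples.** Section 4.2 has follow-up samples kept at the sites until relapse is diagnosed and then analysed retrospectively on the HemaChip. Tables 2 and 3, by contrast, list HemaChip testing at the follow-up visits themselves.

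**Endpoints and developer.** Section 3 makes sensitivity and specificity for each stage primary endpoints. Section 1.2 says that JaxBio holds the exclusive licence and may use the results for marketing approvals.

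**Nearest safeguards.** Samples are to be anonymized (10.2.1), eCRF data are coded (12.4), barcodes are assigned at screening (Table 2), and quality control is to equalise analytic conditions across labs (section 8). None of these is described as hiding the group from the person who runs or reads the chip.

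**The concern.** The inference in section 10.1 does not follow. Discovery compares labelled groups to find markers, so it cannot be done without labels. In validation the label is needed at one step only, when the finished call is set against the reference diagnosis. Until then, knowing the group serves no purpose and opens two routes to bias.

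- **Reading and validity.** Whoever judges whether a run is acceptable, or reads a borderline result, may do so knowing the diagnosis or, for stored samples, the relapse.
- **Repeats.** A negative call in a known myeloma patient, or a positive call in a known control, looks like a reason to use the second tube. A call that agrees with the diagnosis does not. If repeats follow that pattern and replace the first result, errors can only be removed, and both sensitivity and specificity move upward.

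At stake are the primary accuracy endpoints of Stages 2 and 3 and the error rate of any test against the 80% minimum set in section 10.4. Locking the classifier would not remove the second route, because it acts through which result is counted.

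**Working it through.** **1. Inputs from the protocol (section 10.4).** Minimum sensitivity p0 = 0.80; arcsine method; significance level 0.05; power 0.80; expected value for validation 0.85 (the text calls this one a specificity); stated n = 356; planned n about 250 for MM and for NHL, and 100 for each other condition.

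**2. Reproducing the plan's figure.**

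n = [(z₁₋α + z_power) / h]², with h = 2·asin√0.85 − 2·asin√0.80 = 0.1319.

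- One-sided: [(1.645 + 0.842) / 0.1319]² = 355.4, which rounds up to the stated 356.
- Two-sided: 452, which does not match.

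The plan's test is therefore one-sided at 5%, and the illustration uses the same test.

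**3. Assumption not in the protocol.** Let g be the share of all missed cases that are retested and end up counted as correct. The protocol gives no value for g, so it is shown over a range from 0 to 0.50. With true sensitivity exactly 0.80:

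reported sensitivity = 0.80 + 0.20·g

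**4. Chance of wrongly concluding that sensitivity exceeds 80%.**

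- Arcsine: Φ(h·√n − 1.645), with h now taken between the reported value and 0.80.
- Exact binomial: chance of at least 211 correct of 250, or at least 87 correct of 100.

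| g | Reported | n=250 arcsine | n=250 exact | n=100 arcsine | n=100 exact |
|---|---|---|---|---|---|
| 0 | 0.80 | 5.0% | 4.5% | 5.0% | 4.7% |
| 0.05 | 0.81 | 10.6% | 9.6% | 8.2% | 7.6% |
| 0.10 | 0.82 | 20.1% | 18.3% | 12.8% | 11.8% |
| 0.30 | 0.86 | 81.3% | 79.6% | 48.3% | 45.6% |
| 0.50 | 0.90 | 99.8% | 99.8% | 88.4% | 87.6% |

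Example (g = 0.10, n = 250): h = 0.0510; 0.0510 × 15.81 − 1.645 = −0.839; Φ = 0.201.

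**5. Reading g.** It is the product of two shares: misses that are retested, and retests that turn correct and replace the first call. The row g = 0.05 corresponds to 25% × 20%; g = 0.50 needs every miss retested and half of them turning. If retests are chosen without regard to the call, or never replace a valid result, this bias is zero.

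**The case against.** Several points on the other side are fair.

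- **No text describes selective replacement.** The protocol does not say that discordant calls are re-run or that a backup result overwrites the site result. A reader might infer that accuracy is inflated; the documents support only that it can be. This stands.
- **Section 10.1 has a benign reading.** It may mean only that labels are needed to compare calls with diagnoses. But it never limits itself to that step, and no other section masks the reader.
- **Anonymized samples, barcodes and quality control.** These might be applied so as to hide the group. The protocol does not say so, and section 10.1 says the groups are known. That the operator knows the group remains an inference from the open design.
- **The operator need not be the diagnosing team.** The synopsis allows partner labs, and eligibility requires only that patients have been diagnosed. This stands, and the point does not depend on it.
- **Retest rules may sit in the Study Manual or the statistical analysis plan.** Neither is shown, and their absence here is not itself an error. But openness is a design feature that the protocol already fixes, and a later analysis plan cannot mask samples already run.
- **Influence of the chip result on the clinician.** A reader might also infer that clinicians record disease status after seeing the chip result. The documents do not support this. Section 4.2 stores follow-up samples until relapse is diagnosed, and Stage 3 subjects donate once, with their myeloma lab profile scheduled at screening. What remains is an inconsistency between section 4.2 and Tables 2–3.

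**Conclusion.** The point holds as a risk that the design leaves open, not as a demonstrated bias. Section 10.1 carries the need for labels from discovery into validation without reason. Stage 2–3 testing has no stated masking to group, reference result or outcome, and discretionary backup testing has no stated rule on which result is analysed. Stage 1 is not affected, since it has no site chip test and no backup-tube retest. Stage 3 is less exposed than Stage 2, because disease status there is not a pre-assigned group, although the lab profile may be known before the chip is read.

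The size depends entirely on the assumed replacement share. At a true sensitivity of 80% it runs from nothing (no replacement) to +1 point (5% of misses flipped) to +10 points (50%). At n=250 the false-pass risk runs correspondingly from 5% to about 10% to over 99%. No document figure supports any particular value in that range. The change should be made before Stage 2–3 samples are run, because masking cannot be added afterwards.

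**What to change.** 1. In section 10.1, limit the open-label justification to Stage 1.
2. In sections 7.2, 7.3 and 8, Table 2 footnote 9 and Table 3 footnote 2, state for Stages 2–3, including the relapse samples tested retrospectively, that:
   - samples are run and called under barcode only, masked to group, reference result and outcome;
   - the chip call is locked before the label is released;
   - the first technically valid site result is the primary result;
   - the backup tube is tested only after a quality-control failure defined without reference to the call, or in a random subset;
   - all backup tests are logged, reported separately, and never replace a valid site result.
3. Reconcile section 4.2 (samples stored until relapse) with Tables 2–3 (HemaChip at follow-up visits), so that it is clear when follow-up samples are run and what is known at that time.

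**Cost.** Wording in the protocol and Study Manual, and a small amount of coding and data-access work. Barcodes and second tubes already exist, and no patient procedure changes. Reported accuracy may be slightly lower.

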10.2 Statistical methods

All data collected will be summarized and presented. Continuous variables will be described as the mean, median, standard deviation, minimum and maximum. Categorical data will be described with contingency tables including frequency and percentage. Individual patient listings of all data will be generated and presented.

Statistical descriptions and analyses will be carried out using a statistical analysis software.

10.2.1 Study populations

The analyses of the study will be on those patients who were eligible, who have signed a consent form and donated at least one blood sample.

Gender: If available, a similar number of males and females participants will be employed for all stages. Gender differences may be reflected by differential epigenetic patterns. Our mission is to develop a screening and diagnostic tool that will be employed by all genders.

Age group: In general, all participants will be over 18 years old. As epigenetic patterns undergo changes with increasing age, the study will focus on (but not limited to) participants at an age close to the median age at diagnosis, i.e. 55-80 years old. This is applicable with all groups including patients, control, follow-up patients, at risk screening populations and first degree relatives. Aged matched controls will account for age-related changes.

All samples will be anonymized.

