4.1 First stage (discovery phase)

The first stage (discovery phase) will include at least 30 patients from each of the following groups: MM, pre-MM conditions (SMM and MGUS), HL, aggressive NHL (DLBCL), FL, MZL, AML, MDS and control subjects with no malignant disease.

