4.3 Third stage

The last stage consists of screening of a larger group of subjects at risk to develop MM / lymphoproliferative disorder. This stage will include 400 elderly patients (>65 years old) and 500 first-degree relatives of patients (and in particular siblings). The screening, enrollment and sample collection can begin in the first stage of the trial, in order to meet the recruitment goals.

In all stages, the age and sex-matched subgroups will be considered and matched.

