5 STUDY POPULATION

5.1 Number of subjects

First stage: at least 300 subjects.

Second stage: at least 1000 subjects.

Third stage: up to -900 subjects.

The sample size calculations and consideration are presented in section 10.4 below.

The number of participants in the study is described in Table 1 below.

Table 1. Number of participants

	1st Stage	2nd Stage*	3rd Stage*
	No. of Patients/Subjects (at least)	No. of Patients/Subjects (at least)	No. of Patients/Subjects (up to)
MM	30	250	-
MGUS	30	100	-
SMM	30	100	-
HL	30	100	-
DLBCL	30	250	-
FL	30		-
MZL	30		-
AML	30	100	-
MDS	30	100	-
Control (with no malignant disease)	30		
Subjects at risk	-	-	400 Elderly >65 500 First degree relatives

* The screening, enrollment and sample collection can begin in the first stage of the trial, in order to allow a maximum follow-up period for at-risk subjects as part of the study and to meet the recruitment goals.

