10.3 Interim analysis

A single formal interim comparative analysis of the epigenetic patterns in blood-derived DNA from control subjects with no malignant disease and subjects at risk for developing the investigated hematological malignancies and the patterns obtained for all malignant and premalignant hematological conditions will be conducted after approximately 24 months from the beginning of the study and will include:

Comparative analysis for 250 newly diagnosed NHL samples with HemaChip

Comparative analysis for 250 newly diagnosed MM samples with HemaChip

Comparative analysis for 100 samples of the following conditions: SMM, MGUS, HL, AML, MDS, control subjects with no malignant disease and subjects at risk for developing the investigated hematological malignancies.

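### Section 10.2.1 credits age-matched controls with removing age effects, but one shared control group need not match nine disease groups, so age- or sex-related loci may be selected as disease markers

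*Protocol*

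**What the plan says.** Protocol section 10.2.1 recognises that epigenetic patterns change with age and that the sexes may differ. On age it concludes: "Aged matched controls will account for age-related changes". Section 4.3 (and the synopsis, under Methodology) adds: "In all stages, the age and sex-matched subgroups will be considered and matched". Neither place gives a matching ratio, a matching procedure or a covariate adjustment.

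On numbers, section 4.1 says that stage 1 "will include at least 30 patients from each of the following groups", and lists nine disease groups and one control group. Section 5.1 gives the totals: "First stage: at least 300 subjects" and "Second stage: at least 1000 subjects". Table 1 has a single control row, with 30 in stage 1 and nothing in stages 2 and 3. Section 10.3 nevertheless plans a "Comparative analysis for 100 samples of the following conditions: SMM, MGUS, HL, AML, MDS, control subjects with no malignant disease", among others.

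Two further measures bear on comparability. Section 10.2.1 sets a focus on ages 55 to 80 for every group, controls included, but says that it is not a limit. It also aims for similar numbers of men and women where available. Section 5.2.1 admits anyone aged 18 or over.

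**The concern.** A control group has one age-sex distribution. It can be matched to nine disease groups at once only if those nine share that distribution, and nothing binding in the protocol makes them do so. The sentence in section 10.2.1 therefore promises more than the design secures.

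The first primary objective (section 2) asks for markers specific to each condition. That needs contrasts between diseases as well as against controls. Matching controls to patients does not align the ages of two disease groups, however many controls there are.

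If a locus tracks age or sex rather than disease, a residual imbalance can carry it into the marker set. Section 10.4 uses the discovery data to choose the HemaChip markers, so such a locus would pass to the later stages. If validation groups have the same age differences, it could appear to validate. It could then mislead in stage 3, where 400 subjects are chosen for being elderly.

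**Working it through.** **1. Origin of 30 per group.** Section 10.4 uses a one-sample arcsine calculation against a sensitivity of 0.80, with alpha 0.05 and power 0.80:

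n = [(z_alpha + z_power) / (2·asin√p − 2·asin√0.80)]²

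Taking alpha as one-sided (the protocol does not say), p = 0.95 gives [(1.645 + 0.842) / 0.476]² = 27.3. That rounds up to 28, against the stated 30. The same formula reproduces the other 13 rows of the table exactly, for example 99 at 0.89 and 356 at 0.85. So 30 comes from a sensitivity calculation. It says nothing about the size of the control group or about matching.

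**2. Control count.**
- Stage 1: 10 groups × 30 = 300, that is 270 patients and 30 controls.
- Stage 2: 250 (MM) + 250 (NHL) + 5 × 100 = 1000. The patient rows use the whole stated minimum, so no control is counted.
- Interim: 100 control samples are listed without a recruitment number in Table 1.
- Separate 1:1 matched controls for each disease group in stage 1 would need 9 × 30 = 270 controls, against a planned minimum of 30.

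**3. What a residual age gap can do (illustration).** The protocol gives no ages by disease, no age correlation for any locus and no locus-selection rule for this study. All three are assumed here: age correlation r, mean age gap g in within-group SDs, and a two-sided 5% t-test per locus. For a locus with no disease effect, the standardised shift between groups is r × g, and the noncentrality is

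δ = r·g / √(1/30 + 1/30) = r·g / 0.258, with 58 degrees of freedom and critical value 2.002.

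| r | g (SD) | δ | Selected |
|---|---|---|---|
| any | 0 | 0 | 5% |
| 0.2 | 0.25 | 0.19 | 5.4% |
| 0.3 | 0.5 | 0.58 | 9% |
| 0.5 | 0.5 | 0.97 | 16% |
| 0.5 | 1 | 1.94 | 48% |

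A separate calculation with a normal test at |Z| > 2, the threshold used in the preliminary work (section 1.1), gives nearly the same: 8.3%, 15.3% and 47.5% for the last three rows, from a base of 4.6%.

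**4. Cost of adjusting.** For two equal groups whose mean ages differ by g SD, adding age as a covariate multiplies the variance of the group contrast by 1 + g²/4:
- g = 0.5: 1 + 0.0625 = 1.06
- g = 1: 1 + 0.25 = 1.25
- g = 2: 1 + 1 = 2.00

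**The case against.** The strongest objection is that model specification usually belongs in the statistical analysis plan, which section 10.6 mentions and which is not at hand. Nothing in section 10 excludes adjustment, and section 10.2.2 summarises age and sex by group, so an imbalance would be visible. This stands to the extent that the absence of a model is not in itself a fault. It does not rescue the sentence in section 10.2.1, which affirmatively names matched controls as what deals with age.

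Matching is also not the only measure. The 55-80 focus covers every group and the sex balance is a separate aim. Both help, but neither binds.

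The matching line in section 4.3 is not confined to controls and could be read as covering disease-versus-disease subgroups. The wording is too general to settle this, and no method follows it.

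A reader might infer that one control group cannot match nine diseases and that age effects will therefore enter the signatures. The documents do not support that. They give no age or sex distribution by disease, and a common age window could make one group roughly comparable with all nine. Nor is the control group fixed at 30: that is a stage 1 minimum, section 5.5 allows more samples, and the interim lists 100 controls.

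A reader might also carry the illustration over to stage 2 group sizes, where the rates would be higher. Marker selection is mainly a stage 1 step, although section 10.4 allows later tuning, so the 30 v 30 rates are the relevant ones.

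**Conclusion.** The concern holds in a limited form. Section 10.2.1 credits age-matched controls with accounting for age, while the design has one shared control group for nine disease groups and only soft encouragement towards a common age-sex make-up. Disease-versus-disease contrasts are not protected by matched controls at all. Age- or sex-related loci may be selected as disease markers; the documents do not show that they will be.

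The size depends on quantities that the protocol does not give. Under the assumed correlations and gaps, false selection at 30 v 30 runs from barely above 5% (correlation 0.2, gap 0.25 SD) to 48% (correlation 0.5, gap 1 SD). The calculation covers age only. For sex, the point rests on the reasoning about shared distributions. The change is worth making because it is cheap and acts on the step that determines the chip's content.

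**What to change.** In section 10.2.1, replace the sentence that credits matching alone. State that all locus-level marker-selection comparisons, disease versus control and disease versus disease, will be adjusted for age (continuous) and sex. Keep matching and the 55-80 focus as design measures that secure overlap between groups. Matching controls to the pooled patient distribution would not be enough by itself, because the pooled distribution need not resemble that of any single disease.

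The number of stage 2 controls in Table 1 should be reconciled with the 100 control samples listed in section 10.3.

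Age and sex are already recorded (Table 2), so adjustment needs no new data and, where ages overlap, no extra subjects. The cost is a modest loss of precision: contrast variance up about 6% at a 0.5 SD age gap and 25% at 1 SD. Where the ages of two groups barely overlap, the adjusted contrast leans on extrapolation and is unreliable. Those pairs should be reported as such.
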